The uncertainty in the best-evidence practice is also due to the multifactorial aetiology of SSP. The major hypothesis is that a reduction of the space between the acromion and the glenohumeral joint, the so-called subacromial space, causes an encroachment of the soft tissues during arm elevation, often referred to as "shoulder impingement" . The subacromial tissues mainly involved are the rotator cuff (RC) tendons,  encountering degeneration and inflammation . However, this anatomical "impingement" theory does not sufficiently explain the pathophysiology , which in fact displays a multifactorial aetiology. Both intrinsic and extrinsic mechanisms are involved in SSP; the former in terms of degeneration of the tendon itself, the latter in terms of compression of the RC tendons. Intrinsic factors are linked to tendon degeneration, due to the natural process of aging, altered biology, genetic predisposition and tendon mechanical properties . Extrinsic factors originate externally from the RC tendons and include anatomical variants of the acromion, alterations of humeral or scapular kinematics (named scapular dyskinesis), muscle imbalance, postural deviations and soft tissue tightness. In particular, scapular dyskinesis is a key component in the production of symptoms in SSP, in association with muscle imbalance or inadequate activation patterns (i.e. decreased activity of the serratus anterior and lower trapezius, and overactivation of the upper trapezius) . However, the presence of scapular dyskinesis is not always associated with changes in shoulder symptoms and function during and after the rehabilitation. Therefore, the second objective is to investigate whether improvements in shoulder pain, function and quality of life is positively related with reduced presence of scapular dyskinesis.

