# **Scientific Research Objectives**

The primary aim of this project is to provide proof-of-concept for the clinical effectiveness of the "exercising into discomfort" approach in patients with SSP. In the first three objectives, the focus will be on its effect on shoulder pain and functionality (patient-reported outcomes, objective 1), on scapular dyskinesis (objective 2), subacromial space, and the tendon structures (objective 3) during and after 3 months of exercise therapy in patients with SSP. In the fourth objective, the relationship between patient reported outcomes and the US measurements during the treatment course will be explored. Two groups will be compared in a randomized controlled trial (RCT): an intervention group "exercising into discomfort" (G1) and a control group "exercising without discomfort" (G2). The time points of assessment will be prior to the treatment at baseline (T0), at 6 weeks during treatment (T1), end of treatment at 12 weeks (T2), and follow up at 26 weeks (T3).

OBJECTIVE 1	To investigate the effectiveness of exercising into discomfort during a strength training program in the treatment of SSP on self-reported shoulder pain and function
Methods	Double Blind Randomized Controlled Trial comparing 2 groups (G1 versus G2), with SPADI (Shoulder Pain and Disability Index, a valid and reliable patient-reported outcome measure of pain and disability  ) as primary outcome. A "high pain monitoring model" will be used to monitor pain during and 1 hour after every exercise in G1 (see "intervention" in methodology).
Hypothesis	In G1 SPADI will be reduced more than in G2.
Novelty/ Relevance	If successful, the results of this study will lead to a reconceptualization of exercises in SSP, allowing pain (defined as discomfort sensation) to be an essential component and not a barrier in the physiotherapy treatment.

OBJECTIVE 2 ft	To investigate whether improvements in shoulder pain, function and quality of life is positively related with reduced presence of scapular dyskinesis
Methods	Scapular dyskinesis will be registered by visual observation at rest and during movements (abduction and flexion) and its effects on pain will be tested by scapular assistance test and scapular retraction test
Hypothesis	Scapular dyskinesis will decrease more in G1, in relation to the increase in strength and coordination of the scapulothoracic and scapulohumeral muscles.

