# Outcome measures

All outcomes will be measured at baseline (T0) and 6 (T1), 12 (T2), 26 (T3) weeks and the assessors will be blinded to group allocation. The **primary outcome** is the **difference in mean change between groups from T0 to T1, T2 (12 weeks, end of the treatment), and T3 (26 weeks, follow-up)** in the patient self-reported outcome score **Shoulder Pain and Disability Index (SPADI)**. This questionnaire is a patient-reported outcome measure (PROM) with high test–retest reliability and construct validity  and is available and validated in Dutch .

Secondary outcomes are registered for each patient at the same time points as the primary outcome, except for the Global Perceived Effect Score, which will be assessed after 1st treatment and then at 6 and 12 weeks. The secondary outcomes are:

**Scapular dyskinesis:** The procedure we will use is based on the procedures described by Tate et al.  and Struyf et al. . Scapular position will be observed at rest and during active loaded and unloaded humeral motion in a frontal and sagittal plane. The effect of scapular correction will be tested by means of the modified scapular assistance test and scapular retraction test . Reduction of pain during these tests compared with non-assistance during the same tests confirms scapular involvement in the shoulder complaints.

**Subacromial space**: Acromiohumeral distance (AHD) is a US measurement used to quantify the subacromial space. It is defined as the shortest linear distance between the most inferior aspect of the acromion and the humeral head . AHD is measured at 0 and 60 degrees of active shoulder elevation in the scapular plane, following the procedure of measurement indicated by Navarro-Ledesma et al . It has already been used to evaluate different populations, such as healthy volunteers  and patients with shoulder pain .

**Tendon changes**: Tendon structural changes (limited to RC thickness and long biceps) will be evaluated using US device and following international guidelines . STT will be also computed as percentage of subacromial space, known as the occupation ratio (using the formula [(STT/AHD)\*100] .

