# WP3: Data analysis

Statistical analyses will be performed using JMP ®Pro 14.0.0 (SAS Institute Inc., Cary, NC, USA) . Level of significance is set at p= 0.05. Appropriate descriptive statistics will be performed.

**OBJECTIVE 1,2,3:** A mixed regression model for repeated measures will be used to assess both the evolution of SPADI (pain and function), strength, ROM and US parameters within persons from baseline (T0) over time (T1, T2, T3) and the differences in evolution between subjects. Potential confounders are: age, gender, BMI, previous corticosteroid injections, severity of initial symptoms. They will be measured during the history taking at the first assessment and added into the mixed regression model as co-variants. If for a certain variable the percentage of missingness will be more than 15%, multiple imputation for missed observation will be used. There are three assumptions for the mixed regression model: change over time, a sensible measure for time (multiple time points of measure), normality of residuals (it will be checked using a Shapiro-Wilk test). If these residuals are not normally distributed, an appropriate transformation will be performed first. Therefore, this model best fits the longitudinal design of the RCT. **OBJECTIVE 4**: correlation analysis between tendon structures and clinical symptoms using the correlation for pairs of continuous variables in JMP.

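### Objective 2 is assigned to a model that contains no dyskinesis variable, and Objective 4 asks about changes while its analysis reads as correlating values visit by visit

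*Combined protocol and SAP*

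**What the plan says.** **Objective 2.** Under Scientific Research Objectives the aim is an association: "To investigate whether improvements in shoulder pain, function and quality of life is positively related with reduced presence of scapular dyskinesis". The hypothesis row adds a group comparison: "Scapular dyskinesis will decrease more in G1". The rationale gives the motive, namely that "the presence of scapular dyskinesis is not always associated with changes in shoulder symptoms and function during and after the rehabilitation".

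WP3: Data analysis (project application) handles Objectives 1, 2 and 3 with one mixed model for repeated measures, used "to assess both the evolution of SPADI (pain and function), strength, ROM and US parameters within persons". On covariates it says: "Potential confounders are: age, gender, BMI, previous corticosteroid injections, severity of initial symptoms".

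Under Outcome measures, "Scapular position will be observed at rest and during active loaded and unloaded humeral motion in a frontal and sagittal plane". Two symptom tests follow, with a criterion: "Reduction of pain during these tests compared with non-assistance during the same tests confirms scapular involvement in the shoulder complaints". The procedures are taken from cited papers.

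**Objective 4.** The objective row asks whether improvement in pain, function and quality of life is associated with changes in subacromial space and tendon structures. The methods row describes associations between ultrasound parameters and symptoms at T0, T1, T2 and T3. The text introducing the objectives says this relationship will be explored. The whole analysis in WP3 is "correlation analysis between tendon structures and clinical symptoms using the correlation for pairs of continuous variables in JMP".

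**2022 renewal.** The sample size target falls from 54 to 44. Dyskinesis and ultrasound data are to be processed from June 2022, and allocation is to be unblinded only in November 2022.

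**The concern.** An objective needs an analysis that contains its variables and targets its question. Objective 2 has two parts, an association and a group comparison, and the model it is assigned to has dyskinesis on neither side. Someone who followed WP3 exactly would finish with no result for either part.

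Objective 4 raises a different problem. A correlation of values at one visit mixes two things: lasting differences between patients (some people have both a wider space and milder symptoms) and what moves together during treatment. Only the second speaks to the objective row. A value correlation can show a link when changes are unrelated, or miss one when they are linked. WP3 also mentions only tendon structures, although the acromiohumeral distance (AHD) is central to the objective.

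**Working it through.** The documents give no sample size, power or precision for Objectives 2 and 4, so there is no stated figure to reproduce. The 54 and 44 concern SPADI.

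**Step 1: does the Objective 2 model contain its variables?**
- Outcomes listed: SPADI, strength, ROM, ultrasound parameters.
- Covariates listed: age, gender, BMI, previous corticosteroid injections, initial severity.
- Needed for the association: change in dyskinesis, change in SPADI, change in EQ-5D. Dyskinesis and EQ-5D are in neither list.
- Needed for the hypothesis: dyskinesis as an outcome by group. It is not listed.
- The renewal says dyskinesis data will be processed and gives no method.
- The documents do not state the dyskinesis scale or how the rest, loaded and unloaded observations combine. If it is present/absent, a model checked for normal residuals does not fit it.

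**Step 2: values or changes in Objective 4?** The objective row says changes. The methods row includes T0, where no change exists yet, so it reads as values by visit. The pairwise correlation in WP3 reads the same way, although it could be run on change scores.

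**Step 3: does the difference matter?** Inputs: N = 44 (renewal); 44 × 0.85 = 37.4, so 37, using the 15% drop-out from Sample size; alpha 0.05, taken as two-sided. The documents give no variances over time, so I assume that a share s of each measure's variance is stable: 50% or 70%. Let B be the correlation of stable levels and W that of the visit-to-visit parts.

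- Correlation of T2 values = B√(s₁s₂) + W√((1−s₁)(1−s₂)).
- Correlation of T0-to-T2 changes = W.
- Probability of significance ≈ Φ(|atanh r|·√(N−3) − 1.96).

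Changes unrelated (W = 0), N = 44:

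| Stable shares | r of values, B = 0.3 | Significant | r of values, B = 0.5 | Significant |
|---|---|---|---|---|
| 50% / 50% | 0.15 | 16% | 0.25 | 37% |
| 70% / 50% | 0.18 | 21% | 0.30 | 50% |
| 70% / 70% | 0.21 | 28% | 0.35 | 65% |

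Simulation gives 16-28% and about 38-66%. Change scores stay at about 5%. At N = 37 the formula gives 14-24% and 32-57%.

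Changes linked (W = −0.3):
- B = 0: the value correlation is −0.09 to −0.15, detected in 9-16% of trials at N = 44. Change scores: atanh(0.3) × √41 = 1.98, so about 51% (simulated 50-52%); about 43-44% at N = 37.
- B = −0.3: the value correlation is −0.29 to −0.30, so both methods detect it in about 50% at N = 44. The advantage of change scores is gone.

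**Step 4: what could Objective 2 detect?** Compare SPADI change between patients whose dyskinesis lessens (assumed 20-50%) and the rest, at 80% power. Approximately d = 2.80 × √(1/n₁ + 1/n₂). For 22 and 22 this is 0.84 (0.86 with the t distribution); for 9 and 35 it is 1.05 (1.07). Over the range, with the t distribution: 0.86-1.07 SD at N = 44 and 0.95-1.21 SD at N = 37.

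**Step 5: how many tests?** There are three scores (SPADI, EQ-5D index, EQ-5D VAS) and four visits. The five ultrasound measures under Outcome measures give 5 × 3 × 4 = 60 tests, with 60 × 0.05 = 3 expected significant if nothing is linked. The renewal drops only the weighted measures and so appears to keep the coracohumeral and subscapularis ones. That makes eight with the occupation ratio: 8 × 3 × 4 = 96 tests, 4.8 expected.

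**The case against.** The strongest reply has several parts.

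- *Objective 2 is not ignored.* It is listed by number under a repeated-measures model of change over time and between subjects, which is the right form for the group hypothesis. This stands: for that half, the defect is an incomplete outcome list and a scale not stated here. The scale may lie in the cited procedures, so a reader should not infer that the trial has none. The association half still has no analysis.
- *Objective 4's visits are specified.* They are, in the methods row, so it would be wrong to say that the documents name no visit. But this row is what points to values, against the objective row.
- *The simulation rests on chosen assumptions.* It does. A reader might infer that change scores are always more powerful, and Step 3 shows otherwise. The case for them is that they match the stated question.
- *Nothing shows that choices will follow the results.* Correct. Allocation stays blinded until November 2022, so the plan can be completed blind.
- *These are modest aims.* Objective 4 is to be explored, with 37 to 44 patients. That argues against requiring an elaborate within-patient model, but not against naming the variables and the question.

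**Conclusion.** The point holds in a limited form. As written, the plan cannot answer Objective 2. For Objective 4 it most naturally answers a different question from the one in the objective row, and its wording omits subacromial space. Both conclusions rest on the text alone.

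The size for Objective 4 is illustrative. With stable shares of 50-70% and 44 patients, value correlations would be significant in about 16-28% or 38-66% of trials with unrelated changes (stable-level correlation 0.3 or 0.5), against about 5% for change scores. If stable levels are unrelated too, value correlations also stay at 5%. The test count of 60 or 96 depends on which measures are used, which the documents leave open.

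A reader might infer that the trial's main result is in doubt. It is not: these objectives are secondary or exploratory, and the SPADI comparison does not depend on them.

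**What to change.** In WP3: Data analysis:

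1. Add dyskinesis and EQ-5D to the modelled outcomes. State the dyskinesis scale and how the observations combine. If it is categorical, use a logistic or ordinal mixed model, or GEE.
2. Add the Objective 2 association: T0-to-T2 change in dyskinesis as a predictor of change in SPADI and in EQ-5D, adjusted for group, reported as an estimate with a 95% CI.
3. For Objective 4, make the main analysis the group-adjusted association of T0-to-T2 change in each ultrasound measure, AHD and occupation ratio included, with change in SPADI and EQ-5D. Group adjustment keeps a treatment effect on both measures from being read as a link. Keep by-visit value correlations as descriptive. Label the analysis exploratory and state the number of pairs (15 with five ultrasound measures and three scores, 24 with eight). A within-patient mixed model over all four visits is optional.
4. Align the Objective 4 objective and methods rows with this.

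Fix these choices before the unblinding described in the renewal, and label anything added later post hoc.

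The cost is wording and a little more analysis on data already collected. The downside is limited power: about 43-52% for a change correlation of −0.3, and only differences of about 0.9-1.2 SD detectable for Objective 2. Estimates with intervals are therefore more useful than significance tests.

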# Work Plan

Table 1 shows the overall timeline of this four-year project, including the following four work packages (WP): the preparation of the trial (WP1), the RCT (WP2), data analysis (WP3), finalizing PhD (WP4). The main 4 milestones are: fine-tune protocol after feasibility study (M1), end of patients recruitment (M2), end of data analysis (M3), submission and correction of relevant publications (M4).

		Maran		20			1				1		24		1	20			1		~~	
		Year			2019			2020				2021				2022				2023		
		Quarter	1	2	3	4	1	2	3	4	1	2	3	4	1	2	3	4	1	2	3	4
WP1: prep	paration of the trial																					
Task 1.1	Systematic review in exercise in SSP, survey on physiotherapy practice in SSP																					
Task 1.2	Development of intervention protocol																					Γ
Task 1.3	Feasibility study																					
Task 1.4	US training, US reliability study																					
Task 1.5	Fine-tune protocol, ethical approval																					
WP2: RCT																						
Task 2.1	Baseline measurements T0 (0w)																					
Task 2.2	Intervention – T1(6w), T2 (12w)																					
Task 2.3	Follow up – T3 (26w)																					
WP3: Data	a analysis																					
Task 2.1	Data analysis for Objectives 1,2,3,4 (T0,T1,T2)																					Ī
Task 2.2	Data analysis for Objectives 1,2,3,4 (T3)																					
WP4: Fina	lising PhD																					
Task 4.1	Writing articles (systematic review, feasibility stud protocol RCT, RCT)	у,																				
Task 4.2	writing PhD thesis																					
Task 4.3	Submission and defence																					
Milestone	S								M1				M2			M3				M4		

 Table 1 Timeline of 4-year project. WP=Work packages, T0=baseline, T1=6weeks, T2=12weeks, T3=26weeks

### PROJECT OUTLINE – renewal 11/5/2022

### Specify the progress of your PhD project.

If you deviate from the approved application please describe and motivate.

**Table 1** shows the overall timeline, including the following five work packages (WP): the preparation of the trial (WP1), the RCT (WP2), data analysis (WP3), writing articles and finalizing PhD (WP5). The main 4 milestones are: fine-tune protocol after feasibility study (M1), end of patient's recruitment (M2), end of data analysis for RCT (M3), writing PhD dissertation (M4). The project was financed by the University of Antwerp from 1/10/2018 to 30/10/2020 and by the FWO from 1/11/2020 to 31/10/2022. The timeline has been adapted and it is based on recruitment rate for the RCT of the last two years, impacted by the Covid-19 pandemic. Changes compared to the initial FWO project are described in detail below.

**Table 1 Timeline**. The years in orange indicate the funding from DOCPRO (University of Antwerp) and the years in green indicate the funding from FWO. Abbreviations: M=Milestone, PT=physiotherapy, RCT=Randomized Controlled Trial, SSP=Subacromial Shoulder Pain, T0=baseline, T1=9weeks, T2=12weeks, T3=26weeks, US=Ultrasound, WP=Work package. The initial timeline proposed in the FWO project is in light blue, adaptations to the timeline are indicated in dark blue.

### WP1: Preparation of the trial

Development of the intervention for the RCT (WP1: 1.1, 1,2): Aim: develop the intervention protocol for the RCT based on the most recent literature about exercises in subacromial shoulder pain. The intervention protocol was developed by October 2019. Moreover, a survey on current physiotherapy practice in Belgium and the Netherlands was published to serve as a starting point for the intervention (co-authorship, see Publication list). *Status*: completed according to the plan.

US training and US reliability study (WP1: 1.4): Aim: validate the skills of the PhD student as novice sonographer. In August 2019 the PhD student followed a US training during a 4-days research stay supervised by the US expert [name]. In February 2020 the US expert came to Antwerp for a 2-week period to conduct an inter-reliability study on the US parameters previously decided and discussed during the research stay. *Status*: completed according to the plan.

The research stay proposed in the first FWO project in Denmark in September 2020 on the use of the sonoelastography, which is an US feature detecting differences in the elasticity of the soft tissues, was not conducted. It was not possible to measure this feature with the available US machine and the PhD student acquired the necessary US skills already in the reliability study phase performed in February 2020 for the relevant measures for the RCT.

Feasibility study and fine-tune the protocol (WP1, 1.3 1.5): Aim: a feasibility study on exercise into discomfort was performed from November 2019 to May 2020. Status: completed (start delayed compared to FWO initial project, from Q3-2019 to Q4-2019). A critical revision of the protocol for the RCT was performed after the feasibility study, as mentioned in the FWO application. Some changes were necessary to the protocol. 1) Changes to the intervention in the RCT: the intervention in the RCT changed from 4 exercises into discomfort between 4-7 on a Numeric Pain Rating Scale (NPRS, scale 0-10) proposed in the initial FWO application to 1 exercise into discomfort and the 3 remaining exercises performed with no/minimal pain. This modification was necessary after a thorough analysis of the feasibility study and discussion with the physiotherapists and the research team. If this single painful exercise was not provocative anymore (4-7 on NPRS) before 9 weeks, a rate of perceived exertion (Borg Scale) was used instead of the NPRS. In this way, the exercises could be between 4 (somewhat hard) and 7 (very hard) representing more the subjective effort during the exercise than the pain provoked during the exercises. Although this modification could potentially change the comparison between a painful vs. non-painful exercise program, this final decision was taken together with the research team in order to compensate possible deviations from the protocol in the future RCT. 2) Impact of Covid-19 on feasibility study: patients stopped to go to the physiotherapists from March to May 2020 but they continued to exercise at home. Questionnaire were sent online via Qualtrics, therefore subjective data were not lost. Objective measures (i.e. strength and US measures) were lost for 7 patients at follow-up of 6 and/or 12 weeks but available data for patients who went at least 7 out of 9 sessions to the physiotherapists were analysed in order to adjust the protocol for the RCT. Milestone 1 (ethical approval on amendments to the protocol and fine-tune the protocol for the RCT): completed according to the plan.

